### 6.2 Visit 3 (Week 12± 5 days)

- a) LPPAI score
- b) Review changes to medical history and current medications
- c) Screen/Review adverse events
- d) Repeat photographs
- e) Assessments of hair density using phototrichograms
- f) Dispense 3 tubes and reconcile study drug
- g) Review compliance
- h) Urine Pregnancy Test (female patients of childbearing potential); confirm form of contraception

### 6.3 Visit 4 (Week 24± 5 days)

- a) LPPAI score final
- b) PGA score final
- c) DLQI score final
- d) Review changes to medical history and current medications
- e) Screen/review adverse events
- f) Repeat photographs
- g) Assessments of hair density using phototrichograms
- h) Reconcile and collection of unused study drug
- i) Urine Pregnancy Test (female patients of childbearing potential); confirm form of contraception

Study Activity	Schedule of Events			
	Day 1 SCREENING BASELINE	Week 4 PHONE FOLLOW- UP	Week 12 FOLLOWUP	Week 24 FOLLOWUP
Visit Number	1	2	3	4
Allowable visit window in days		+/- 5	+/- 5	+/- 5
Review Eligibility	X			
Informed Consent	X			
Medical History	X			
Dispense/Reconcile Medications	X	X	X	X
Review Changes to Med History and Medications			X	X
LPPAI	X		X	X
PGA	X			X
DLQI	X			X
B-HCG (females)	X		X	X
Photographs/Hair Count	X		X	X
Review Valchlor Application Instructions	X		X	X
Screening for Adverse Events		X	X	X

## **7 Statistical Plan**

### **7.1 Sample Size Determination**

Due to the pilot nature of the study, no formal statistical power or sample size calculations are necessary. The sample size of 20 patients will be sufficient for this pilot study to obtain a preliminary estimate of treatment efficacy and to generate data that will be useful in the design of a larger study.

### **7.2 Statistical Methods**

#### **Descriptive Statistics**

Continuous variables will be summarized using the sample mean, median, standard deviation, interquartile range, and range. Categorical variables will be summarized using number and percentage of patients

#### **Handling of Missing Data**

This is a prospective study and therefore we do not anticipate any missing data. In the event of any unexpected missing data, no attempt to impute this missing data will be made; missing data will simply be treated as missing in the statistical analysis.

#### **Multiplicity**

Since this is an exploratory pilot study, no adjustment for multiple testing is needed.

#### **Primary Hypothesis:**

The primary endpoint for this study is the LPPAI score. While a minimal clinically significant difference for this outcome measure has not been established, clinically meaningful treatment responses will generate large changes in the LPPAI score given the weightings used in the underlying formula. Therefore, the proposed minimal accrual target of twenty patients will be adequate for the preliminary data generating purposes of an exploratory study. A larger sample size to detect smaller changes in the LPPAI score is not needed as small differences in the LPPAI score are not clinically meaningful. The minimal accrual target of 10 is achievable given an estimated incidence of LPP/FAA of 1-3% in tertiary hair loss centers. The definitions of complete response, partial response, and non-response will be defined using standardized LLPAI scoring which will permit a relative comparison of treatment efficacy to previously published systemic treatments using hydroxychloroquine and mycophenolate mofetil.

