**Study Summary**

Title	Valchlor in the Treatment of Lichen Planopilaris: A Single Arm, Open-Label, Exploratory Study
Running Title	Valchlor in the treatment of Lichen Planopilaris
Protocol Number	16-006731
Phase	Pilot Study
Methodology	Open-Label, Exploratory Study
Overall Study Duration	14 Months
Subject Participation Duration	6 months
Single or Multi-Site	Single
Objectives	To investigate the efficacy of Valchlor in the treatment of LPP.
Number of Subjects	20
Diagnosis and Main Inclusion Criteria	Adults patient with active LPP or FFA 1) 18 years old or older at time of consent 2) Biopsy proven diagnosis of LPP or FAA
Study Product, Dose, Route, Regimen	Valchlor gel, average use one 60 gram tube per month
Duration of Administration	6 months
Reference therapy	Valchlor gel
Statistical Methodology	The primary endpoint for this study is the LPPAI score. While a minimal clinically significant difference for this outcome measure has not been established, clinically meaningful treatment responses will generate large changes in the LPPAI score given the weightings used in the underlying formula. Therefore, the proposed accrual target of twenty patients will be adequate for the preliminary data generating purposes of an exploratory study.

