## 4.4 Early Withdrawal of Subjects

### 4.4.1 When and How to Withdraw Subjects

Patients are free to withdraw at any time and for whatever reason. No data will be collected for withdrawn subjects and withdrawn subjects may be replaced within the accrual period. There will be no follow-up for withdrawn subjects. Pre-specified reasons for discontinuing include, but are not limited to, the following:

- Patient Request: Patient decided that he/she did not want to continue (for any reason)
- Adverse Event: Patient experienced a related or unrelated event that would interfere with the study objectives/evaluation
- Lost to Follow-up: Patient did not come in for a visit and could not be reached by phone
- Treatment Failure: If in the Principal Investigator and/or Investigators' judgment, the patient's condition required another form of treatment
- Mechlorethamine sensitization: Patient develops contact dermatitis to Valchlor that cannot be managed with low potency topical corticosteroids
- Inclusion/Exclusion Discrepancy/Violation: Patient should not have been enrolled
- Noncompliance: Patient is not complying with the protocol requirements (i.e. visit schedule, dosing, regimen, etc.); a patient is to be withdrawn if he/she misses two consecutive visits
- Other: Any other reason

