## **Data Quality Assurance**

Once the study is completed the Principal Investigator will randomly select 3 participants and compare the data documented for each on the CRF with what is entered into the REDCap database. If there is any discrepancy, the Principal Investigator and/or Investigators will cross-reference all 20 patients to ensure accuracy.

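### The all-treated response rate becomes a completer rate because withdrawn participants have no 6-month LPPAI and no rule counts them; no interval is planned, and a stray accrual figure of 10 needs correcting

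*Combined protocol and SAP*

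**What the plan says.** **Outcome.** Section 3.4 defines the primary outcome as the percent reduction in LPPAI from baseline after 6 months, classed as complete, partial or non-response.

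**Population.** Section 7.3 includes each participant who received study drug, whether or not they withdrew, and adds a sensitivity analysis that leaves out those who withdrew.

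**Withdrawals.** Section 4.4.1 states: "No data will be collected for withdrawn subjects and withdrawn subjects may be replaced within the accrual period". Its listed reasons for discontinuing include treatment failure and contact dermatitis that cannot be managed. Section 4.4.2 adds that no further contact will be attempted.

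**Missing data.** Section 7.2 expects none and, if some occur, rules out imputation and leaves them missing.

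**Reporting.** Section 7.2 says: "Categorical variables will be summarized using number and percentage of patients". No confidence interval is planned anywhere. Section 7.1 states: "The sample size of 20 patients will be sufficient for this pilot study to obtain a preliminary estimate of treatment efficacy", with a larger study in view. Section 7.2 says that the response definitions "will permit a relative comparison of treatment efficacy to previously published systemic treatments".

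**Accrual figure.** Under Primary Hypothesis, section 7.2 says that "the proposed minimal accrual target of twenty patients will be adequate for the preliminary data generating purposes of an exploratory study". Two sentences later it says: "The minimal accrual target of 10 is achievable given an estimated incidence of LPP/FAA of 1-3% in tertiary hair loss centers". The Study Summary says that "the proposed accrual target of twenty patients will be adequate", section 3.2 gives twenty, and the quality check in section 9.3 would "cross-reference all 20 patients to ensure accuracy".

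**The concern.** Each of the three rules is ordinary on its own, but they do not fit together. Section 7.3 promises an analysis of everyone treated. Section 4.4.1 ensures that withdrawn participants have no 6-month LPPAI, and the missing-data rule gives them no category. A table of number and percentage then has only completers to count.

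This matters because some reasons for leaving are related to outcome. If participants who leave for treatment failure or unmanaged dermatitis vanish from the denominator, the reported rate can look better than the experience of those treated. Replacement hides the loss further, since the table can still show 20 evaluable participants. The figure is meant to inform a larger study and to be read against published treatments, and no interval would show how loosely 20 patients fix it.

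The figure of 10 is a separate and lesser matter. It carries the same label as the twenty in the same paragraph and is not explained.

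**Working it through.** **1. The plan's own figure.** There is no calculation to reproduce. Section 7.1 waives a formal sample size calculation, and the documents give no target precision, expected response rate or withdrawal rate.

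**2. Tracing one withdrawn participant.** The participant received drug, so section 7.3 includes them. Under sections 4.4.1 and 4.4.2 there is no 6-month LPPAI. A participant who left after the week 12 visit has a score from that visit, but the outcome is defined at 6 months and imputation is excluded, so that score cannot stand in. The participant has no response category. No sentence says whether they stay in the denominator. If missing is simply missing, they do not.

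**3. Effect on the sensitivity analysis.** Section 7.3 would then exclude withdrawn participants who are already absent from the primary rate, so the two results largely coincide. Any difference would have to come from the rare withdrawn participant who does have a 6-month score.

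**4. Size.** Assumptions, not taken from the documents: 8 responders, and *w* = 1, 4 or 6 withdrawals, none with a 6-month LPPAI.

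- Without replacement: evaluable rate = 8/(20 − *w*); all-treated rate = 8/20.
- With replacement up to 20 evaluable: evaluable rate = 8/20; all-treated rate = 8/(20 + *w*).

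Exact (Clopper-Pearson) 95% intervals are in brackets.

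| Withdrawals | Evaluable, not replaced | All treated, not replaced | Evaluable, replaced | All treated, replaced |
|---|---|---|---|---|
| 1 | 8/19 = 42% (20–67%) | 8/20 = 40% (19–64%) | 8/20 = 40% (19–64%) | 8/21 = 38% (18–62%) |
| 4 | 8/16 = 50% (25–75%) | 8/20 = 40% (19–64%) | 8/20 = 40% (19–64%) | 8/24 = 33% (16–55%) |
| 6 | 8/14 = 57% (29–82%) | 8/20 = 40% (19–64%) | 8/20 = 40% (19–64%) | 8/26 = 31% (14–52%) |

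The gap runs from about 2 points to 17 points without replacement, and from about 2 to 9 points with it. The evaluable rate can never be the lower of the two, because the numerator is the same and the denominator is smaller.

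**5. Precision.** Even with complete data, 8/20 has an exact 95% interval of 19% to 64%, a width of about 45 points. A bare 40% does not show this.

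**6. The accrual figure.** The Study Summary and sections 3.2, 7.1 and 9.3 all use 20, as does the first statement under Primary Hypothesis in 7.2. Only one sentence uses 10, and no analysis or decision refers to it.

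**The case against.** **Section 7.3 already names the population.** This is true: the plan does have a denominator. What is missing is narrower, namely how a treated participant without a 6-month LPPAI is counted within it.

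**The effect may be small.** This also stands. One withdrawal moves the rate by about 2 points, and the documents give no basis for expecting more.

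**Keeping unassessed participants in the denominator is itself a form of imputation.** Numerically it treats them as non-responders, which conflicts with the current missing-data sentence. That sentence therefore has to be amended openly. The resulting rate is also a floor: with 4 of 20 unassessed and 8 responders, the unobserved truth lies between 8/20 = 40% and 12/20 = 60%.

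**It is an exploratory pilot with no planned test, and a reader can compute an interval from the counts.** This is fair, and nothing here asks for power or more patients. But estimation is the stated purpose, and a reader can compute the right interval only if the denominator is clear. Section 7.2 also plans mean, median and spread for continuous variables, so percent LPPAI reduction will be described. Those summaries meet the same missing scores and do not settle the response rate.

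**Stronger readings of the 10.** A reader might infer that the sample size is undetermined, or that recruitment is infeasible. The documents support neither. Twenty is used consistently elsewhere, and no clinic volume is given from which infeasibility could be shown.

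**Conclusion.** The concern holds in a limited form. Read together, sections 4.4.1, 7.2 and 7.3 turn an analysis described as all-treated into one of completers, and they leave the planned sensitivity analysis with little to test. The rate among evaluable participants would exceed the all-treated rate by about 2 to 17 points in the illustrations above. That range rests on assumed counts of 8 responders and 1 to 6 withdrawals, and on reading missing as dropped from the denominator, which the text implies but does not state.

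A reader might go further and infer that the reported response will be biased upward. The documents do not establish that. It depends on whether anyone withdraws and on whether those who do would have responded less often; the listed withdrawal reasons make this plausible, not certain.

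The missing interval is a smaller gap that the same edit closes. The figure of 10 is a wording correction with no effect on any result.

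**What to change.** In sections 7.2 and 7.3:

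- Report complete response, and complete plus partial response, each with a Clopper-Pearson 95% interval, over all participants who received study drug, including any later replaced.
- State that participants without a 6-month LPPAI are counted as not having a documented response, and show their number in a separate row.
- Amend the missing-data sentence in 7.2 to allow this for the response rate.
- Define the 7.3 sensitivity analysis as the same two rates among participants with a 6-month LPPAI.
- Describe the comparison with published treatments as descriptive, with the interval beside it.

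As a minor edit under Primary Hypothesis, change the 10 to agree with 20 or, if a lower minimum is intended, label it as a separate figure.

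The cost is a few sentences, two intervals and one table row, with no extra patients or visits. The downsides are that the headline percentage is lower if anyone withdraws, it may understate response if some of those who left had improved, and the interval will look wide.

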### **3 Study Design**

#### **3.1 General Description**

This is a single arm, open label, exploratory study to evaluate the efficacy of Valchlor in the treatment of LPP. Subjects will be screened by the Department of Dermatology at the Mayo Clinic in Florida outpatient clinic and interested qualified subjects will be consented and offered participation. This study is designed to establish feasibility and proof of concept and will not include randomization or crossover components.

Patients with biopsy proven LPP who have failed one prior topical or systemic therapy with evidence of active disease will be eligible to participate. The presence of active disease will be based on a baseline clinical exam showing perifollicular erythema with scaling. Patients with predominance of end stage scarring hair loss but without significant active erythema will be excluded. Involvement restricted to the frontal scalp is a recognized clinical variant of LPP and is known as frontal fibrosing alopecia (FAA). As the histological features of LPP and FAA are identical, patients with FAA subtype of LPP would also be eligible to participate in the study.

Eligible participants using high-potency topical corticosteroids, intralesional corticosteroids, or oral hydroxychloroquine may enroll but will be required to discontinue use during the study period.

All study participants will apply Valchlor 0.016% gel to involved areas at night, beginning with three times a week (Mondays, Wednesdays and Fridays) and increasing to daily application after one month, if well tolerated. Patients will be instructed to first part the hair away from involved area as needed, limit application to areas with alopecia and erythema, apply 30 minutes after showering or washing, and allow treated areas to dry for 5 to 10 minutes before covering with clothing or going to bed. Participants will be instructed to wash their hands with soap and water after applying Valchlor. Caregivers who assist in application will be instructed to wear disposable nitrile gloves when applying Valchlor and dispose with the household trash. Patients will be instructed to store Valchlor in the refrigerator away from foods at 36°F - 46°F and apply within 30 minutes after removing from refrigeration.

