## **5.3 Method for Assigning Subjects to Treatment Groups**

This is an open-label pilot investigation and all study participants are assigned to active treatment with a topically applied study drug. There is no placebo arm in this study.

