## **5.8 Masking/Blinding of Study**

This is an open-label pilot investigation. Masking and blinding procedures are not applicable. Qualitative and quantitative evaluations of response to treatment will be recorded. Updated photographs will be included in participants' records at each visit.

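### Section 7.2 says the LPPAI response classes will allow an efficacy comparison with published hydroxychloroquine and mycophenolate results, but the plan shows no basis for that comparison and about 20 patients could not resolve moderate differences

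*Combined protocol and SAP*

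**What the plan says.** Section 3.4 sorts patients by percent reduction in LPPAI at 6 months: complete response above 85%, partial response 25 to 85%, non-response below 25%. Section 7.2, under Primary Hypothesis, gives these classes a use beyond describing the cohort: they are standardised, "which will permit a relative comparison of treatment efficacy to previously published systemic treatments using hydroxychloroquine and mycophenolate mofetil". The sentence carries no caveat, and none about cross-study comparison appears elsewhere.

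The rest of the plan describes something narrower:

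- Section 3.1: "This is a single arm, open label, exploratory study to evaluate the efficacy of Valchlor in the treatment of LPP", and "This study is designed to establish feasibility and proof of concept and will not include randomization or crossover components".
- Section 5.3: "There is no placebo arm in this study".
- Section 5.8: "Masking and blinding procedures are not applicable".
- Section 7.1: no power calculation; 20 patients are held sufficient "to obtain a preliminary estimate of treatment efficacy".
- Section 7.2, Descriptive Statistics: categorical variables are summarised by count and percentage. No interval is mentioned.

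The hydroxychloroquine and mycophenolate papers appear in the reference list. The documents do not report their response rates, sizes, populations, follow-up or methods of assessment.

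**The concern.** Comparing a response rate with a published one needs more than the same cut-offs. It needs patients with a similar outlook, similar assessment and follow-up, and enough precision to separate a real difference from chance. The plan addresses none of these.

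Two features of this study could matter. Section 3.1 admits patients "who have failed one prior topical or systemic therapy with evidence of active disease", so the cohort is selected on treatment history and on current activity. Selecting on activity also invites regression to the mean, which a single arm cannot separate from drug effect. And the LPPAI is built from graded symptoms and signs plus two yes/no items, all scored without masking.

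At stake is interpretation. As the sentence stands, a bare percentage from about 20 patients could be set beside a published percentage and reported as better or worse than a named drug, with the protocol cited as having said this was possible.

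**Working it through.** **Inputs from the documents.** n = 20 (Study Summary; sections 3.2 and 7.1); the response classes of section 3.4; counts and percentages as the only planned summary (section 7.2). The plan gives no alpha, power, effect size or benchmark rate, so there is no calculation of its own to reproduce.

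**Assumed inputs.** Every historical and true response rate below is an assumption, shown over a range because the documents give none. Alpha is taken as 0.05 two-sided, that is, an upper tail of at most 0.025.

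**Step 1: precision of the study's own rate.** The exact (Clopper-Pearson) 95% interval for x responders out of n runs from the 2.5% quantile of Beta(x, n − x + 1) to the 97.5% quantile of Beta(x + 1, n − x).

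| Responders | Observed | Exact 95% interval | Width |
|---|---|---|---|
| 6/20 | 30% | 11.9% to 54.3% | 42 points |
| 10/20 | 50% | 27.2% to 72.8% | 46 points |
| 14/20 | 70% | 45.7% to 88.1% | 42 points |

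**Step 2: power against a fixed benchmark.** Treat the historical rate p0 as known without error, which favours the plan. Take the smallest r with P(X ≥ r) ≤ 0.025 for X ~ Binomial(20, p0). Power at a true rate p1 is P(X ≥ r) for X ~ Binomial(20, p1).

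| Assumed p0 | Rule | Upper-tail alpha | True p1 | Power |
|---|---|---|---|---|
| 10% | ≥ 6/20 | 0.011 | 30% | 58% |
| 10% | ≥ 6/20 | 0.011 | 40% | 87% |
| 30% | ≥ 11/20 | 0.017 | 50% | 41% |
| 30% | ≥ 11/20 | 0.017 | 60% | 76% |
| 50% | ≥ 15/20 | 0.021 | 70% | 42% |
| 50% | ≥ 15/20 | 0.021 | 80% | 80% |

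A 20-point difference has 41% to 58% power over this range; a 30-point difference has 76% to 87%.

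**Step 3: allow for error in the historical rate.** Assume a published series of 20 and ignore all bias. With the normal approximation for two proportions, power = Φ[(d − 1.96·se0)/se1], where se0 uses the pooled rate and se1 the separate rates.

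- 50% versus 70%: pooled rate 0.60; se0 = √(0.60 × 0.40 × 2/20) = 0.155; se1 = √((0.25 + 0.21)/20) = 0.152; (0.20 − 1.96 × 0.155)/0.152 ≈ −0.68; power about 25%.
- 50% versus 80%: pooled rate 0.65; se0 = √(0.65 × 0.35 × 2/20) = 0.151; se1 = √((0.25 + 0.16)/20) = 0.143; (0.30 − 1.96 × 0.151)/0.143 ≈ 0.03; power about 51%.

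**Step 4: what the arithmetic leaves out.** Steps 2 and 3 address chance only. They treat the two sets of patients as exchangeable, which the documents give no means of checking.

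**The case against.** The strongest reply is that no comparison is actually planned. The sentence names no test, benchmark or decision rule; it can be read as explaining why a standard scale was chosen. The plan calls itself exploratory throughout, and its summaries are descriptive. This stands in part: no planned analysis is in error, no estimate changes, and n = 20 is not wrong for a pilot. A descriptive side-by-side display on a common scale is also legitimate. But the sentence promises a comparison of efficacy with named drugs, without qualification, and the exploratory label is a reason to limit that promise.

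Four stronger readings are tempting, and the documents do not support them.

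- *Chance alone would cover almost any plausible difference.* Step 2 contradicts this: 30-point differences against a fixed benchmark have 76% to 87% power. Section 7.2 itself says that only large LPPAI changes matter, and section 1.1 says conventional treatments generally do not bring remission, so a low complete-response benchmark is credible.
- *The published rates are known not to be comparable.* The documents do not describe those series. Prior treatment failure and open-label scoring distort the comparison only if the series differ in these respects. Comparability is undemonstrated, not disproved.
- *Replacing withdrawn patients inflates the rate.* Section 4.4.1 does say that "withdrawn subjects may be replaced within the accrual period", but section 7.3 keeps everyone who received study drug in the primary analysis. How that fits with collecting no data on withdrawn patients is a separate question.
- *Precision should be judged at n = 10.* Section 7.2 mentions 10 once, but also twenty, which is the figure used elsewhere. That inconsistency is a separate matter.

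**Conclusion.** The concern holds as an overclaim about interpretation that should be corrected. The plan attributes to its response classes a comparative use for which it gives no benchmark, comparator population or method, in one unblinded arm of about 20 patients.

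An observed 50% would be compatible with true rates from 27% to 73%. With an assumed, error-free historical rate, 20-point differences are more likely missed than found in two of the three cases examined, and found only 58% of the time in the third. Differences of 30 points are usually detectable on chance grounds, but power for 50% versus 80% drops from 80% to about 51% once the benchmark itself comes from an assumed 20 patients. Even a clear difference could reflect patient selection, regression to the mean or unblinded scoring.

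The interval depends only on n = 20 and the observed count. The power figures rest on assumed rates and an assumed two-sided 5% level. The conclusion that comparability is undemonstrated rests on what the documents omit and needs no assumption about the published studies.

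**What to change.** In section 7.2, Primary Hypothesis, replace the comparison clause with: *published response rates will be cited as descriptive context only, and no inference about relative efficacy will be made.* In the statistical methods, add that the complete response rate and the complete-plus-partial response rate will each be reported with an exact 95% confidence interval. Clopper-Pearson is one suitable choice.

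This is one sentence of wording and two intervals. Sample size, data collection and study procedures do not change. The intervals also serve the aim in section 7.1 of informing a larger study better than a bare percentage would. The downside is a more modest stated conclusion: the report could show the published rates alongside its own but could not rank the treatments.
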